7.6.3. Reduction of response using PR-PCSS and CR-PCSS after Retreatment

The proportion of subjects with reduction of response (refer to section 4.4.1) will be summarized using frequency counts and percentages using TRR Population after Retreatment by subject category (ie, Category I and II, and Overall) and treatment area (ie, left and/or buttock) at all observation visits after retreatment where cellulite assessments has been performed.

The proportions will be computed based upon number of subjects within each category and treatment area retreated prior to that visit.

The following efficacy end points for reduction of response will be summarized:

- Proportion of subjects with 2-level composite reduction
- Proportion of subjects with 1-level composite reduction
- Proportion of subjects with 2-level reduction on either scale
- Proportion of subjects with 1-level reduction on either scale
- Proportion of subjects with complete loss of response

The time to composite reduction of response (ie, by 1-level and 2-level separately), time to partial response and time to complete loss of response (refer to section 4.4.1 for derivation) will be summarized descriptively using TRR Population after Retreatment.

The listings of cellulite PR-PCSS and CR-PCSS severity ratings will be provided for subjects in OLR Population after Retreatment.

7.6.4. Improvement of Response using PR-PCSS and CR-PCSS

The improvement of response in cellulite severity is assessed in the open-label study for the subjects who received retreatment. The cellulite severity assessment during retreatment phase will be used for this analysis. The proportion of subjects with improvement in response compared to cellulite assessments at Day 1 prior to retreatment (refer to section **Error! Reference source not found.**) will be summarized using frequency counts and percentages using OLR Population by subject category (ie, Category I and II, and Overall) and treatment area (ie, separately for left and right buttock) at Day 22, 43, and 71 following retreatment:

- Proportion of 2-level composite responders
- Proportion of 1-level composite responders
- Proportion of 1-level and 2-level CR-PCSS responders
- Proportion of 1-level and 2-level PR-PCSS responders

The above responder analysis will be repeated considering Day 1 of double blinded study as reference.

The listings of cellulite PR-PCSS and CR-PCSS severity ratings will be provided for subjects in OLR Population after Retreatment.

7.6.5. Changes in the PR-CIS Scores from Baseline

The PR-CIS scores (Each item, total, and abbreviated) will be analyzed separately at Day 180 using Day-180 Observational Population and Prior to Day 180 Population, for the data before retreatment using TRR Population Before Retreatment, and OLNLR Population and data for after retreatment using OLR Population.

At Day 180 Evaluation

The observed and/or change from baseline in PR-CIS item scores, total, and abbreviated scores (refer to section 4.4.3) of the subjects in 180 – Day Observational Population will be summarized descriptively by treatment arm (ie, CCH 1.68 mg, Placebo, and Overall) at overall treatment area

(ie, two buttocks). The Screening assessments done at Day 71/EOS visit in the double-blind studies will be used as baseline.

Also, the observed and/or change from Day 1 of double blind studies (302/303) in PR-CIS item scores, total, and abbreviated scores (refer to section 4.4.3) of the subjects up to Day 180 in 180–Day Observational Population and Prior to Day 180 Population will be summarized descriptively by treatment arm (ie, CCH 1.68 mg, Placebo, and Overall) at overall treatment area (ie, two buttocks).

Before Retreatment

The observed and/or change from baseline and change from Day 1 of double-blinded studies in PR-CIS item scores, total, and abbreviated scores (refer to section 4.4.3) of the subjects who did not receive retreatment and the data until the point prior to retreatment for the subjects who are retreated will be summarized descriptively using TRR Population Before Retreatment and OLNLR Population by subject category (ie, Category I and II, and Overall) at overall treatment area (ie, two buttocks) and assessment visits: Day 180, Month 12, 18, 24, and 36.

The Screening assessments done at Day 71/EOS visit in the double-blind studies will be used as baseline.

Also, the observed and/or change from Day 1 of double blind studies (302/303) in PR-CIS item scores, total, and abbreviated scores (refer to section 4.4.3) of the subjects who did not receive retreatment and the data until the point prior to retreatment for the subjects in TRR Population and OLNLR Population will be summarized descriptively by subject category (ie, Category I and II, and Overall) at overall treatment area (ie, two buttocks).

After Retreatment

The observed and/or change from baseline in PR-CIS item scores, total and abbreviated scores (refer to section 4.4.3) from Day 71 of the retreatment session and other observational visits of the subjects who are retreated in the open label study will be summarized descriptively using OLR Population by subject category (ie, Category I and II, and Overall) at overall treatment area (ie, two buttocks).

The Screening assessments (ie, Screening B) done during the retreatment phase in the open label study will be used as baseline.

The listings of PR-CIS scores for each item along with total and abbreviated scores will be provided separately for All Subjects prior to retreatment and for subjects in OLR Population after Retreatment.

7.6.6. Changes in the PR-CIS Scores from Day 71 Open-label Period

The PR-CIS scores (each item, total, and abbreviated) will also be analyzed for the observational period after retreatment using OLR Population.

The observed and/or change in PR-CIS item scores, total and abbreviated scores (refer to section 4.4.3) at observational visits after retreatment compared to Day 71/End of Treatment Session in open label retreatment phase will be summarized descriptively using OLR Population

by subject category (ie, Category I and II, and Overall) at overall treatment area (ie, two buttocks).

The listings of PR-CIS scores for each item along with total and abbreviated scores will be provided separately for subjects in OLR Population after retreatment.

7.6.7. Responder Analysis based on Baseline PR-CIS Scores

The PR-CIS responders (Each item, Total, and Abbreviated) will be analyzed separately at Day 180 using Day-180 Observational Population, for the data before retreatment using TRR Population Before Retreatment, and data after retreatment using OLR Population.

At Day 180 Evaluation

The proportion of PR-CIS responders based on item scores, total, and abbreviated scores (refer to section 4.4.3) of the subjects in 180 – Day Observational Population will be summarized using frequency counts and percentages by treatment arm (ie, CCH 1.68 mg, Placebo, and Overall) at overall treatment area (ie, two buttocks).

Before Retreatment

The proportion of PR-CIS responders based on item scores, total, and abbreviated scores (refer to section 4.4.3) of the subjects who did not receive retreatment and the data until the point prior to retreatment for the subjects who are retreated will be summarized using frequency counts and percentages for subjects in TRR Population Before Retreatment by subject category (ie, Category I and II, and Overall) at overall treatment area (ie, two buttocks) and assessment visits: Day 180, Month 12, 18, 24, and 36.

After Retreatment

The proportion of PR-CIS responders based on item scores, total and abbreviated scores (ie, based on scores as compared to baseline - refer to section 4.4.3) at Day 71 of the retreatment session and other observational visits of the subjects who are retreated in the open label study will be summarized using frequency counts and percentages for subjects in OLR Population by subject category (ie, Category I and II, and Overall) at overall treatment area (ie, two buttocks).

7.6.8. Responder Analysis based on Day 71 Open-label Period PR-CIS Scores

The proportion of PR-CIS responders based on item scores, total and abbreviated scores (ie, based on scores as compared to Day 71 of open-label period - refer to section 4.4.3) at observational visits after retreatment will be summarized using frequency counts and percentages for subjects in OLR Population by subject category (ie, Category I and II, and Overall) at overall treatment area (ie, two buttocks).

7.6.9. Responder Analysis at each level of improvement in the S-GAIS

The S-GAIS ratings and S-GAIS responders will be analyzed separately up to Day 180 using Day-180 Observational Population, for the data before retreatment using TRR Population Before Retreatment, and data after retreatment using OLR Population.

At Day 180 Evaluation

The proportion of S-GAIS responders (1-level and 2-level) and S-GAIS ratings (-3 to +3) (refer to section 4.4.4) of the subjects in 180 – Day Observational Population will be summarized using frequency counts and percentages by treatment arm (ie, CCH 1.68 mg and Placebo, and Overall) at treatment area (ie, separately for left and right buttock).

Before Retreatment

The S-GAIS response of the subjects who are not-retreated and until the point prior to retreatment for the subjects who are retreated will be evaluated.

The proportion of S-GAIS responders (1-level and 2-level) and S-GAIS ratings (-3 to +3) (refer to SAP section 4.4.4) will be summarized using frequency counts and percentages for subjects in TRR Population Before Retreatment by subject category (ie, Category I and II, and Overall) at treatment area (ie, separately for left and right buttock) and any visits in this study: Day 180, Month 12, 18, 24, and 36.

After Retreatment

The proportion of S-GAIS responders (1-level and 2-level) and S-GAIS ratings (-3 to +3) (refer to SAP section 4.4.4) at Day 71 and other observational visits of the subjects who are retreated in the open label study will be summarized using frequency counts and percentages for subjects in OLR population by subject category (ie, Category I and II, and Overall) at treatment area (ie, separately for left and right buttock).

The listings of subject response for S-GAIS assessments will be provided separately for All Subjects prior to retreatment and for subjects in OLR Population after retreatment.

7.6.10. Responder Analysis in Subject Satisfaction with Cellulite Treatment

The responders in subject satisfaction with cellulite treatment assessments and individual item ratings will be analyzed separately up to Day 180 using Day-180 Observational Population, for the data before retreatment using TRR Population Before Retreatment, and data after retreatment using OLR Population.

Up to Day 180 Evaluation

The proportion of responders in subject satisfaction with cellulite treatment assessments and individual item ratings (-2 to +2) (refer to section 4.4.5) of the subjects in 180 – Day Observational Population will be summarized using frequency counts and percentages by treatment arm (ie, CCH 1.68 mg and Placebo, and Overall) at overall treatment area (ie, two buttocks).

Before Retreatment

The response of the subjects who are not-retreated and until the point prior to retreatment for the subjects who are retreated will be evaluated.

The proportion of responders in subject satisfaction with cellulite treatment assessments and individual item ratings (-2 to +2) (refer to SAP section 4.4.5) will be summarized using frequency counts and percentages for subjects in TRR Population Before Retreatment by subject

category (ie, Category I and II, and Overall) at overall treatment area (ie, two buttocks) and any visits in this study: Day 180, Month 12, 18, 24, and 36.

After Retreatment

The proportion of responders in subject satisfaction with cellulite treatment assessments and individual item ratings (-2 to +2) (refer to SAP section 4.4.5) at Day 71 and other observational visits of the subjects who are retreated in the open label study will be summarized using frequency counts and percentages for subjects in OLR population by subject category (ie, Category I and II, and Overall) at overall treatment area (ie, two buttocks).

The listings of subject satisfaction with cellulite treatment assessments will be provided separately for All Subjects prior to retreatment and for subjects in OLR population after retreatment.

7.6.11. Proportion of subjects at each level of improvement in the SSRS

The SSRS responders and individual item ratings will be analyzed separately at Day 180 using Day-180 Observational Population, for the data before retreatment using TRR Population Before Retreatment, and data after retreatment using OLR Population.

At Day 180 Evaluation

The proportion of SSRS responders (1-level and 2-level) and individual item ratings (0 to 6) (refer to section 4.4.6) of the subjects in 180 – Day Observational Population will be summarized using frequency counts and percentages by treatment arm (ie, CCH 1.68 mg and Placebo, and Overall) at overall treatment area (ie, two buttocks).

Before Retreatment

The SSRS response of the subjects who are not-retreated and until the point prior to retreatment for the subjects who are retreated will be evaluated.

The proportion of SSRS responders (1-level and 2-level) and individual item ratings (0 to 6) (refer to SAP section 4.4.6) will be summarized using frequency counts and percentages for subjects in TRR Population Before Retreatment by subject category (ie, Category I and II, and Overall) at overall treatment area (ie, two buttocks) and any visits in this study: Day 180, Month 12, 18, 24, and 36.

After Retreatment

The proportion of SSRS responders (1-level and 2-level) and individual item ratings (0 to 6) (refer to SAP section 4.4.6) at Day 71 and other observational visits of the subjects who are retreated in the open-label study will be summarized using frequency counts and percentages for subjects in OLR population by subject category (ie, Category I and II, and Overall) at overall treatment area (ie, two buttocks).

The listings of subject response for SSRS assessments will be provided separately for All Subjects prior to retreatment and for subjects in OLR Population after retreatment.

7.7. Safety Analyses

Safety data for subjects who entered the Open-label Period of the study will be summarized separately before retreatment using Open-label Observation Population, and after retreatment using OLR Population. Safety data from screening to Day 180 will be summarized using Day-180 Observational Population.

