2. STUDY OBJECTIVES

2.1. Primary Objective

The primary objectives of this study are to assess:

- The long-term safety of CCH in the treatment of EFP commonly known as cellulite in adult women
- The safety of CCH when used for retreatment in the treatment of EFP commonly known as cellulite in adult women
- The long-term immunogenicity profile of CCH following treatment of EFP commonly known as cellulite in adult women

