3. STUDY DESIGN AND MEASURES

3.1. Study Design

This is a Phase 3b, long-term open-label extension study to be performed at multiple centers in the United States (US), the study will enroll the subjects who participated in, and completed the previous double-blind, placebo-controlled Phase 3 cellulite studies EN3835-302 or EN3835-303. The objectives of this open-label extension study are to evaluate safety, immunogenicity profile, and temporal pattern of response of CCH in the treatment of EFP.

This study will initially enroll up to approximately 840 subjects until the double-blind studies are unblinded, after which only subjects who received active EN3835 will remain in observation in the current study.

The eligibility of the subjects for this study will be assessed during the Day 71 visit of the respective double-blind trial in which the subject participated. Subjects will be offered enrollment into this trial to observe and record continued evaluation of response to CCH and/or safety for a period of up to 3 years after their Day 71 visit in the double-blind study EN3835-302

or EN3835-303. The assessments made within 14 days of the subject's Day 71/End of Study (EOS) of the double-blind study, will serve as initial screening for the current open-label extension study. If the EN3835-304 screening visit is performed greater than 14 days after the subject's Day 71 of the double-blind study, then only the unique Screening Visit assessments will be performed (informed consent, inclusion and exclusion criteria evaluation, height, weight, and physical examination) separately for the open-label study as mentioned in schedule of events [Table 1](#). No subject will be allowed to enroll in the study if the Screening Visit does not occur within 180 days after Day 71 of Study EN3835-302/303.

At the time of entry into the open-label study and at Visit 1 (Day 180) of study EN3835-304 (approximately 6 months after Day 71 of study EN3835-302/303), the subjects, Investigators and site personnel will remain blinded to the study drug received in the double-blind studies. Even if the EN3835-302/303 study drug blind is broken by the Sponsor; subjects, Investigators and site personnel in study EN3835-304 will remain blinded until after Day 180 safety and cellulite severity assessments of each treatment area are completed.

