3.6. Determination of Sample Size

The study will rollover subjects who completed the respective double-blind studies and are willing to participate in the current study until the double-blind studies are unblinded, after which only active subjects (approximately 420 subjects who received CCH in the double-blind study) will remain in observation in this study. The sample size of approximately 420 should be adequate to determine long-term safety and time to reduction of response to CCH.

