5. ANALYSIS POPULATIONS

The study will use following analyses population for data summarization.

Table 16: Analysis Population

Population	Definition	Displays
Day-180 Observational Population	The Day-180 Observational Population includes all rollover subjects from studies EN3835-302/303.	The protocol deviations, demographic characteristics and safety analysis for the data obtained from Screening to Day 180 will be based on this population. The reduction of response, complete loss of response, and all cellulite assessments (ie, changes in CR-/PR-PCSS, PR-CIS, S-GAIS, SSRS, and subject satisfaction with cellulite treatment at Day 180 will be summarized.
Prior to Day 180 Population	Prior to Day 180 Population includes all subjects who did not meet inclusion criteria #2 or inclusion criteria #5 or those who withdrew from the study due to SAE/AE, or lost to follow-up prior to Day 180.	The protocol deviations, demographic characteristics and safety analysis for the data obtained from Screening to Day 180 will be based on this population.
Open Label Observation Population	The Open Label Observation Population includes all subjects who enter the open-label study and received active CCH in EN3835-302 or EN3835-303. This population will include all Category I, II, and III subjects including the subjects who received retreatment in the Open-label Period.	The protocol deviations, demographic characteristics and safety parameters for the open label period prior to retreatment will be summarized based on this population.
Time to Reduction of Response (TRR) Population Before Retreatment	The TRR Population Before Retreatment includes all subjects who have at least a 1-level or 2-level improvement in both CR-PCSS and PR-PCSS ratings during the double-blind study for either/both treated buttocks. This population will include Category I and II subjects. Reduction of response will be evaluated separately for subjects who have at least a 1-level and 2-level improvement in both CR-PCSS and PR-PCSS ratings during the double-blind study in each treated buttock. The reduction of response prior to retreatment will be analyzed using this population.	The analyses of cellulite assessments prior to retreatment, and demographic characteristics will be based on this population.

Table 16: Analysis Population (Continued)

Population	Definition	Displays

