8. CHANGE FROM PROTOCOL

This SAP is prepared based on the study protocol, original version dated 31-Jan-2018, Amendment 1 dated 19-Apr-2018, Amendment 2 dated 01-Nov-2018, and Amendment 3 dated 14-Jan-2021.

The changes in SAP from what is proposed in protocol is explained in Table 18 below:

Table 18: Changes from Protocol

Text in Protocol	Change in SAP	Justification

Overall Safety Population: All safety analyses will be based on this population. In addition, the safety data will be summarized by treatment period for those retreated subjects with EN3835.
	
Overall Safety Population is renamed as “Open-label Observation Population”
	
Safety profile in this study will be analyzed in two different phases, prior to retreatment phase and after retreatment phase. Hence these populations are defined.
 
The data prior to retreatment will be summarized based on Open-label Observation Population, and data after retreatment will be summarized based on Open-label Retreated Population (Refer to section 5).

TRR Population: The TRR population is defined as all subjects who have at least a 1-level or 2-level improvement in both CR-PCSS and PR-PCSS ratings during the double-blind study for either/both treated buttocks. This population will include Category I and II subjects. TRR will be evaluated separately for subjects who had a 1-level and 2-level composite improvement in CR-PCSS and PR-PCSS during studies EN3835-302/303 in each buttock.
	
Instead of TRR Population, it is renamed as ‘TRR Population Before Retreatment’
	
Reduction of Response will be assessed separately for prior to retreatment and after retreatment. Hence these populations are defined.
 
TRR Population Before Retreatment will include the subjects who are not-retreated and until the point prior to retreatment for the subjects who are retreated (Refer to section 5).
 
TRR Population After retreatment will only include the subjects who are retreated in this study and have at least 1 level or 2 level improvement in both CR-PCSS and PR-PCSS ratings at Day 71/End of Treatment Session in the open label retreatment phase (Refer to section 5).

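### The SAP calls the Overall Safety Population renamed but uses it for safety only before retreatment, and it names no AE table that counts each CCH subject once over the whole follow-up

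*SAP*

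**What the plan says.** The first primary objective (section 2.1) is "The long-term safety of CCH in the treatment of EFP commonly known as cellulite in adult women". Safety of retreatment is listed as a second, separate objective. Section 3.1 sets follow-up "for a period of up to 3 years after their Day 71 visit in the double-blind study", and section 3.6 puts the group that stays under observation at "approximately 420 subjects who received CCH in the double-blind study".

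Table 18 in section 8 gives the protocol text: "All safety analyses will be based on this population. In addition, the safety data will be summarized by treatment period for those retreated subjects with" the study drug. The column for the SAP's change begins "Overall Safety Population is renamed as" and gives the new name, Open-label Observation Population. The justification cell of the same row then says that this population serves the data before retreatment and the Open-label Retreated (OLR) Population the data after it.

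Table 16 defines the Open Label Observation Population as all Category I, II and III subjects, "including the subjects who received retreatment in the Open-label Period", but assigns it safety data only up to retreatment. Section 7.7 repeats this: open-label safety data "will be summarized separately before retreatment using Open-label Observation Population, and after retreatment using OLR Population". Safety from screening to Day 180 is a further summary on the Day-180 Observational Population.

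**The concern.** As quoted, the protocol asks for two things: an analysis of everyone, and an extra breakdown for the retreated. In the SAP the breakdown has taken the place of the overall analysis, and the change column records only a new name.

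The long-term safety objective invites a simple question: of the women treated with CCH, how many had an AE, an SAE, an AE of special interest or a related AE during follow-up? If every AE table covers only one stretch of time, a woman with events in two stretches appears in two tables. The subject counts then cannot in general be combined, and each table's percentage describes only its own stretch.

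**Working it through.** **Step 1. Map each AE summary in section 7.7.2 to its population and time window.**

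| Set | Time covered | Subjects | Drug-related AE summary listed? |
|---|---|---|---|
| 1. 180-day observation | Screening to start of the Open-label Period, plus events ongoing from the double-blind studies | Rollover subjects, by double-blind arm | Yes (related to 302/303 drug) |
| 2. Before retreatment | Start of the Open-label Period to retreatment for retreated women; to the end for Category III and never-retreated women | Category I, II, III | No |
| 3. During and after retreatment | Retreatment onward | OLR only | Yes |

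Two phrases in the third set could be mistaken for a pooled table. Its *Total* column is defined as Treatment Sessions 1 to 3 plus observation after Day 71 of retreatment. Its reference to all study periods sits inside a summary of AEs recorded after retreatment. Neither reaches back before retreatment. The rule that a subject is counted once per SOC and PT works within a table, not across the three sets.

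**Step 2. Denominator of set 2.** Retreated women belong to the population but contribute no events once retreated, and no person-time is planned. The percentage is therefore not a cumulative incidence over a common period.

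**Step 3. Illustration of size.** The plan has no figure to reproduce: 420 is a rollover count with no precision calculation. The number retreated, the timing and the event rates are not given, so these are assumptions: N = 420; follow-up months 0 to 36; Open-label Period starting at month 6; constant hazard; no dropout; a share f of 25%, 50% or 75% retreated at month r = 6.5, 12 or 24; true 36-month incidence p of 5% or 30%.

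With h = −ln(1 − p)/36 and c(t) = 1 − exp(−ht):
- set 1 shows c(6);
- set 2 shows (1 − f)·c(30) + f·c(r − 6);
- set 3 shows c(36 − r), among the 420f retreated;
- the added counts are 420·c(6) + 420·(set 2) + 420f·c(36 − r).

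Example, p = 30%: h = 0.3567/36 = 0.00991, so c(6) = 5.8%. With f = 75% and r = 6.5, set 2 = 0.25 × 0.2571 + 0.75 × 0.0049 = 6.8%.

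| Assumed p | Set 1 | Set 2 | Set 3 | Added counts | True count |
|---|---|---|---|---|---|
| 30% | 5.8% | 6.8% to 23.4% | 11.2% to 25.3% | 132 to 138 | 126 |
| 5% | 0.9% | 1.1% to 3.8% | 1.7% to 4.1% | about 21 | 21 |

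Person-time in set 2 is 420 × [(1 − f)·30 + f·(r − 6)]/12. This runs from 276 person-years (f = 75%, r = 6.5) to 945 (f = 25%, r = 24), of 420 × 3 = 1,260 in total.

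**Step 4. Limits without a model.** Suppose set 2 shows 20% and set 3 shows 30% (both assumed). The combined open-label proportion lies between max(0.20, 0.30f) and 0.20 + 0.30f. That is 20.0% to 27.5% with 25% retreated, and 22.5% to 42.5% with 75% retreated. The ends are extremes: full overlap and no overlap.

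**The case against.** The case for the plan is substantial.

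- **The split is disclosed.** The justification cell in Table 18 states it. A reader might infer a concealed change; the document does not support that. The fault is the word chosen in the change column, and the loss of the overall analysis.
- **The objective does not specify a 3-year incidence.** It says long-term safety. Separate tables suit two separate objectives and keep events after a second course apart from those after the first. This is a good reason to keep the split, but not a reason to drop the overall summary that the quoted protocol text puts first.
- **The information is not lost.** Listings of AEs, SAEs and AEs of special interest are planned, so distinct subjects can be counted by hand. Occurrence counts are planned in every AE summary table, and numbers of new events can be added. Deaths and study discontinuations happen once per woman, so those subject counts add too.
- **For rare events, adding subject counts is nearly exact.** Step 3 shows this at 5%, provided events in different periods are unrelated. The wide limits in Step 4 need extreme overlap patterns on assumed rates and should not be read as the expected error.
- **Not everyone is split three ways.** Category III and never-retreated women are divided only at the start of the Open-label Period.
- **The narrowing concerns safety tables.** The same population also serves disposition, demographics and concomitant medication, where sections 7.1, 7.3 and 7.5 do not repeat the limit.
- **The table shells in SAP Module 2 are not at hand**, so a pooled table might exist there.

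All of these stand as limits. None supplies, in the SAP text, a table that counts each CCH subject once.

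**Conclusion.** The point holds in a limited form. For safety, the SAP narrows the use of a population that it describes as renamed. No AE summary that it names gives the overall proportion of CCH-treated subjects with any AE, SAE, AE of special interest or related AE over the whole follow-up.

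The gap is clearest for related AEs, because the before-retreatment set lists no such summary; even adding the tables would leave that stretch empty. It is moderate for common AEs: in the 30% illustration, adding counts overstates the number of affected women by about 6 to 12 of 126, and no single set shows a figure near 30%. It is small for rare events and absent for deaths and study discontinuations.

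A reader might infer that long-term safety cannot be assessed at all. That goes too far, since the data are collected, tabulated by period and listed. The conclusion rests on the SAP text without its shells, and the sizes rest on the stated assumptions about retreatment and event rates.

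**What to change.** Keep the split tables. Add one overall AE summary, and SOC/PT tables for any AE, SAE, AE of special interest and related AE, for all CCH-treated subjects from double-blind Day 71 to last contact. Count each subject once, give person-years, and flag events after retreatment because they follow a second course. State whether events imported as ongoing from the double-blind studies are included. In Table 18, describe the row as a change of use.

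The cost is one extra set of tables from data already held and one reworded row. The drawback is that the overall tables pool one-course and two-course exposure; the flag and the retained split tables deal with that.
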